16.3. Adjustments for Covariates

No covariate adjustment will be made in the primary and secondary efficacy and immunogenicity endpoint analyses. In order to evaluate a potential effect of covariates,

subgroup analyses will be performed for factors including maternal age stratification (18-28 years of age and 29-40 years of age), the World Bank income categories (low and middle income countries and high income countries), the interval between the immunization and delivery (\leq 30 days and $>$ 30 days), the GA at delivery (pre-term and full term), and by race/ethnicity. Additional subgroup analyses may also be performed.

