3 STUDY DESIGN

3.1 Design

This is a randomized, observer-blind, placebo-controlled trial enrolling up to approximately 4,600 third-trimester pregnant women in the Northern and Southern hemispheres. Randomization will be configured to provide approximately 3,000 exposures to the active test article.

Healthy women in the third trimester of a singleton uncomplicated pregnancy, at low risk of obstetrical complications, and ≥ 18 to ≤ 40 years of age (lower limit of 18 years and 0 days and an upper limit of 40 years and 0 days) will be enrolled and randomized, initially in a 1:1 ratio, into one of two treatment groups, active or placebo, over approximately the three months prior to peak RSV season as shown in [Table 1](#). After the first global season of enrollment, the randomization scheme will be changed to a 2:1 (active / placebo) ratio to enable more efficient accrual of the safety database. Due to the importance of infant RSV exposure in order to demonstrate efficacy of the maternal immunization strategy, investigators will be instructed to base maternal enrollment on a projected date of delivery for each maternal subject. The estimated date of the earliest delivery (EDD-E) will be approximately 6 weeks prior to the historic average onset date of increased RSV transmission at each study site. The estimated date of the latest delivery (EDD-L) will be calculated based on the historic average end date of RSV transmission at each study site, such that participating infants are likely to have a minimum 3 month exposure to RSV transmission. The Sponsor will assist and provide guidance to each site in determining the EDD-E and EDD-L using best available site-specific, local, state/provincial, or national surveillance data to the extent available. Please refer to the **Study Operations Manual** for further details.

Table 1: Treatment Assignments

Treatment Group	Target Maternal Subjects/Group ^[1]	Test Article	Dosing Volume	Vaccination Day
A	~ 1562	Placebo	0.5 mL	Day 0
B	~ 3038	RSV F vaccine		

[1] The target number of subjects that may be enrolled over multiple global RSV seasons, based on a 1:1 randomization for the first season and 2:1 (active / placebo) randomization for all subsequent seasons.

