Section 10.6	Text has been corrected to reflect that all unsolicited AEs for maternal subjects through 180 days post-delivery by severity and relatedness, will be captured.

Location of Change	Change/Modification in Version 9.0
Synopsis, Section 10.8	
The estimated enrollment projections per global season used for the simulation scenarios have been updated, as shown below:
 
Estimated enrollment projections per global season used for the simulation scenarios and operating characteristics were 174 (20 in Northern Hemisphere and 154 in Southern Hemisphere) in global season 1 and 1,304 (210 in Northern Hemisphere and 1094 in Southern Hemisphere); 2,735 (1,220 in Northern Hemisphere and 1,515 in Southern Hemisphere); 3,025 (1,510 in Northern Hemisphere and 1,515 in Southern Hemisphere); and 3,025 (1,500 in Northern Hemisphere and 1,515 in Southern Hemisphere) in subsequent seasons 2, 3, 4, and 5, respectively. The Southern Hemisphere enrollment estimate for the global season 5 was used for the operating characteristics determination for lower than projected enrollment rates.
 
An updated table with simulation scenarios and operating characteristics needed to satisfy the study efficacy objective, has been provided.

Section 10.10.1	
It has been specified that the sequence of formal interim analyses for efficacy will be conditioned by the US FDA requirement that not less than 3,000 actively-immunized maternal subjects and their infants (approximately 4,600 mother-infant pairs in total) be included in the first formal interim.
 
Further specifications have been provided for the conduct of formal interim analyses.

Section 10.10.2	
The section has been inserted to indicate that the Sponsor may trigger the performance of an informational analysis of efficacy as defined in the SAP. This analysis will be performed by the DSMB biostatistician and the IBG in a manner entirely analogous to the analyses for efficacy and futility, and will address a success criterion to be specified in the SAP. The DSMB will communicate the results of the analysis to the Sponsor only in terms of fulfillment or non-fulfillment of the target criterion.

General	Minor changes have been made to improve the readability of the document.

Protocol Version 8.0, 23 August 2016 (revised from 7.0, 15 July 2016)

The following is a summary of the changes made to this protocol.

Location of Change	Change/Modification in Version 8.0

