Healthy women in the third trimester of a singleton uncomplicated pregnancy, at low risk of obstetrical complications, and ≥ 18 to ≤ 40 years of age (lower limit of 18 years and 0 days and an upper limit of 40 years and 0 days) will be enrolled and randomized initially in a 1:1 ratio, into one of two treatment groups, active or placebo, over approximately the 3 months prior to peak RSV season, as shown in [Table 1](#). After the first global season of enrollment, the randomization scheme will be changed from a 1:1 (active:placebo) ratio to a 2:1 (active : placebo) ratio to enable more efficient accrual of the safety database. Due to the importance of infant RSV exposure in order to demonstrate efficacy of the maternal immunization strategy, investigators will be instructed to base maternal enrollment on a projected date of delivery for each maternal subject. The estimated date of the earliest delivery (EDD-E) will be approximately 6 weeks prior to the historic average onset date of increased RSV transmission at each study site. The estimated date of the latest delivery (EDD-L) will be calculated based

on the historic average end date of RSV transmission at each study site, such that participating infants are likely to have a minimum 3 month exposure to RSV transmission. The Sponsor will assist and provide guidance to each site in determining the EDD-E and EDD-L using best available site-specific, local, state/provincial, or national surveillance data to the extent available. The trial will begin with enrollment of women in the Northern hemisphere, followed by enrollment in the Southern hemisphere for the first global RSV season.

Table 1: Treatment Assignments

Treatment Group	Target Maternal Subjects/Group ^[1]	Test Article	Dosing Volume	Vaccination Day
A	~1562	Saline placebo	0.5 mL	Day 0
B	~3038	RSV F vaccine		

^[1] The target number of subjects that may be enrolled over multiple global RSV seasons, based on a 1:1 randomization for the first season and 2:1 (active / placebo) randomization for all subsequent seasons.

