10.3. Analysis of Primary Efficacy Endpoints

The primary efficacy endpoint will be analyzed on the ITT-EFF-I and PP-EFF-I (infant) Populations. Conclusions concerning stopping for futility, the informational analysis, or declaration of attainment of the primary efficacy endpoint at the completion of the study, will only be based on the PP-EFF-I Population. In addition, supportive analyses based on the ITT-EFF-I Population will also be performed.

The Vaccine Efficacy (VE) is defined as $VE (\%) = (1 - RR) \times 100$, where RR = Relative Risk of incidence rates between the two treatment groups (RSV F Vaccine / Placebo). The final analysis will be carried out at one-sided Type I error rate of 0.0124 (i.e., the lower bound of two-sided 97.52% confidence interval). An estimate of vaccine efficacy will be reported using a two-sided 95% confidence interval. This conservative Type I error rate was determined as a part of the original group sequential design (GSD) approach and will be retained to guard against a potential Type I error inflation resulting from the decision to stop the study at ~4,600 maternal subjects given this decision occurred after the informational analysis. Since this change was not part of the original study design at the initiation of the study, the agreement on how to implement the change with respect to Type I error rate was finalized in consultation with the US-FDA.

For the original design using the GSD, a simulation of 5,000 trials was performed under a range of scenarios (including both varying placebo rates of medically-significant RSV LRTI and endpoint event ratios in infants of active vaccinees relative to placebo recipients). A summary of the simulation results is provided in the adaptive design for reference ([APPENDIX 1](#)).

The RR and its CI will be estimated using Poisson regression with Robust error variance [[Zou 2004](#)]. The generalized linear model with unstructured correlation matrix (Robust error variances) will be used. The explanatory variables in the model will include the treatment group. The dependent variable will be the incidence rate of the endpoint of interest. The Robust error variances will be estimated using repeated statement and the subject identifier. Poisson distribution will be used with a link function logarithm.

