13. SAMPLE SIZE CONSIDERATIONS

This study is designed to enroll approximately 4,600 total maternal subjects that include a minimum of 3,000 RSV F vaccine recipients over 4 global RSV seasons.

Assuming a medically-significant RSV LRTI incident rate of 4% in the placebo group and a vaccine efficacy of 65%, then the power of the design to claim success is 87%. [Table 3](#) summarizes the power for different placebo attack rates and vaccine efficacies. Power calculations were performed using the normal approximation (NCSS PASS 14). An estimated PP population size of 4,218 total evaluable infant subjects (2,786 in the RSV F vaccine group and 1,432 in the placebo group to account for 1:1 and 2:1 randomization ratios in Year 1 and the subsequent years, respectively) was used for all calculations.

The target sample size of the safety and efficacy database in third-trimester pregnancy that will be required for licensure is at least 3,000 actively-immunized maternal subjects and their infants. Therefore, the final analysis for efficacy will commence only after a total of 3,000 subjects have been enrolled in the active treatment arm. If no events of a given class are observed among the 3,000 subjects receiving the RSV F vaccine, an approximation to the one-sided upper 95% confidence bound on the rate of SAE occurrence would be 0.1%.

Table 3: Power Calculations for the Primary Efficacy Endpoint (Medically-Significant RSV LRTI Through 90 Days)

Placebo Event Rate	True Event Ratio	Efficacy (1-RR)	Power ^[1]
0.02	0.5	50%	17%
	0.4	60%	41%
	0.35	65%	57%
	0.3	70%	72%
	0.2	80%	92%
0.03	0.5	50%	26%
	0.4	60%	59%
	0.35	65%	76%
	0.3	70%	88%
	0.2	80%	99%
0.04	0.5	50%	34%
	0.4	60%	73%
	0.35	65%	87%
	0.3	70%	96%

Table 3: Power Calculations for the Primary Efficacy Endpoint (Medically-Significant RSV LRTI Through 90 Days)

Placebo Event Rate	True Event Ratio	Efficacy (1-RR)	Power ^[1]
0.05	0.2	80%	>99%
	0.5	50%	42%
	0.4	60%	83%
	0.35	65%	94%
	0.3	70%	99%
	0.2	80%	>99%
0.06	0.5	50%	50%
	0.4	60%	90%
	0.35	65%	97%
	0.3	70%	>99%
	0.2	80%	>99%

^[1] Estimated using normal approximation to rule out H0: Vaccine Efficacy < 30% using one-sided Type I error rate of 0.0124.

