1.0 Introduction

This document outlines the adaptive design for the randomized, adequate and well-controlled, confirmatory trial for demonstrating the superiority of the vaccine in preventing RSV disease in infants via ante-partum maternal immunization. The purpose of this document is to provide a description of the design along with details of the statistical models and simulation results.

This trial is a randomized study, comparing the efficacy of RSV vaccine against placebo. The primary efficacy endpoint is the RSV event rate for the infants under maternal immunization with the vaccine, relative to placebo, referred to as the *event ratio*. We define an RSV event as the occurrence of a protocol-defined medically significant RSV lower respiratory tract infection outcome for the infant, within 3 months of birth. The primary hypothesis of interest is to show super-superiority of the RSV vaccine over placebo. In particular, the primary analysis is to demonstrate that the event ratio is less than or equal to an event ratio target of 0.70.

Enrollment in the study will occur within two different geographic hemispheres per year. Enrollment will take place in the northern and southern hemispheres, prior to and during the typical RSV seasons for those hemispheres. This leads to two "hemispheric" seasons of data, which combine to provide a "global season" of data within an approximate calendar year. During enrollment of the northern hemisphere within the first year subjects will be randomized 1:1 to vaccine or placebo and 2:1 thereafter.

The maximum study size is 8,618 subjects in total across northern and southern hemispheres. However, the sample size required to demonstrate efficacy on the primary endpoint might be smaller. Therefore, an adaptive design is proposed that will allow multiple interim analyses in order to enable early demonstration of the primary efficacy endpoint. Rules are also created for futility interim analyses.

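### Allocation changed from 1:1 to 2:1 after the first global season, but the vaccine efficacy models pool both periods with treatment as the only term, so a different season-1 attack rate biases the relative risk and moves the test off its 0.0124 level

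*SAP*

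**What the plan says.** Protocol 3.1 sets the change in ratio: "After the first global season of enrollment, the randomization scheme will be changed to a 2:1 (active / placebo) ratio". SAP section 2 says the same. SAP Appendix 1, section 1.0, differs: "During enrollment of the northern hemisphere within the first year subjects will be randomized 1:1 to vaccine or placebo and 2:1 thereafter".

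For the primary endpoint, SAP 10.3 specifies a robust-variance Poisson regression and says "The explanatory variables in the model will include the treatment group". No other term is listed. SAP 10.4 repeats this for the secondary endpoints, and protocol 10.4.3 matches. SAP 16.3 closes the door on anything further: "No covariate adjustment will be made in the primary and secondary efficacy and immunogenicity endpoint analyses".

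The subgroups named in SAP 16.3 are maternal age, income category, immunisation-to-delivery interval, gestational age and race/ethnicity. The sensitivity analyses in SAP 10.3 and 16.8 are Kaplan-Meier, the handling of missing specimens and visits, and a tipping-point grid. None uses season or allocation period.

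On the level of the test, SAP 10.3 says "The final analysis will be carried out at one-sided Type I error rate of 0.0124".

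**The concern.** Randomisation makes the arms comparable within an allocation period. Once the ratio changes, the pooled arms contain different mixtures of periods. If the attack rate also differs between periods, the crude relative risk is confounded by period. Stratifying randomisation by site and maternal age does not cure this, because the ratio itself changed over time and neither stratum is in the model.

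Unequal rates are plausible from the trial's own history. The change history for protocol version 9.0 (July 2017) shows that timed respiratory counts and a repeat visit at 2 to 3 days were brought in because, over the first two years, cases were seen by sites without meeting the endpoint and then hospitalised without study assessment. Poorer early capture would lower the first-season rate and bias against the vaccine. Season intensity, or the mostly Southern make-up of projected first-season enrolment, could push either way.

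At stake are the decisive test against 30% efficacy, the parallel test against 0% for submissions outside the US, and the secondary efficacy estimates. The simulations in SAP Appendix 1 use one placebo rate per scenario, so their type I error figures say nothing about this.

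**Working it through.** **Inputs.** Target arms: 1,562 placebo and 3,038 vaccine (SAP Table 1). Per-protocol infants: "2,786 in the RSV F vaccine group and 1,432 in the placebo group", 4,218 in total (SAP 13). Planning case: 4% placebo rate, 65% efficacy, margin RR 0.70, one-sided 0.0124, stated power 87%. Assumed: k, the first-season attack rate divided by the later rate.

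**1. Reproduce the stated power.** On the log scale, SE = √[(1−0.014)/(2,786×0.014) + (1−0.04)/(1,432×0.04)] = 0.205. Then ln(0.70/0.35)/0.205 − 2.244 = 1.14, which gives 87.2%. A score-type approximation gives 87.5%. Both agree with 87%.

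**2. Size of the 1:1 period.** Solve n/2 + (N−n)/3 = placebo count, so n = 6×placebo − 2×N.
- Mothers: 6×1,562 − 2×4,600 = 172.
- Per-protocol infants: 6×1,432 − 2×4,218 = 156, or 78 per arm (3.7% of 4,218).
- Check: SAP Appendix 1, Table 3, projects 20 Northern plus 154 Southern = 174 in the first global season. 174/2 + 4,426/3 = 1,562, the placebo target. If only the 20 Northern women were 1:1, it would be 10 + 4,580/3 = 1,537. The targets fit the global-season reading.

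**3. Bias.** First-season shares are f0 = 78/1,432 = 5.4% (placebo) and f1 = 78/2,786 = 2.8% (vaccine). The crude RR is multiplied by (1 + f1(k−1)) / (1 + f0(k−1)). These denominators are common to all infant endpoints, so the factor also applies to a secondary endpoint with the same k.

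**4. Error of the crude test.** Exact enumeration of the log-RR Wald test, true RR 0.70, overall placebo rate fixed at 4%. The stratified column is a two-period Mantel-Haenszel RR, 2,000,000 simulated trials per row.

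| k | Factor on RR | A true VE of 30% reads as | Error, crude | Error, stratified |
|---|---|---|---|---|
| 0.5 | 1.014 | 29.0% | 0.0100 | 0.0124 |
| 1 | 1.000 | 30.0% | 0.0124 | 0.0124 |
| 1.33 | 0.991 | 30.6% | 0.0141 | 0.0125 |
| 1.5 | 0.987 | 30.9% | 0.0150 | 0.0124 |
| 2 | 0.975 | 31.8% | 0.0180 | 0.0124 |

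The third column is 1 − 0.70×factor. For example, 1 − 0.70×1.014 = 29.0%.

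A robust Poisson model with a period term, 300,000 trials per k, gives 0.0122 to 0.0126. If instead the later rate is held at 4%, the crude error is 0.0101, 0.0151 and 0.0182 at k = 0.5, 1.5 and 2, and 0.0258 at k = 3.

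**5. Null of 0% efficacy (later rate 4%, simulated).** The crude error is 0.0133 at k = 1 and 0.0199 at k = 2. The stratified test stays at 0.0130 to 0.0132.

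**6. Power at 65% efficacy, 4% rate, k = 1 (simulated).** 87.9% crude, 87.7% stratified.

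**7. If Appendix 1 were right** and only the 20 Northern women were 1:1, the crude error at k = 2 would be 0.0130.

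**The case against.** The strongest reply is about weight. The 0.0124 level was carried over from a three-look design and only one efficacy analysis remains. The overall target in SAP 16.4 is 0.025, and every error in the table is below it. At a 4% overall rate, k = 2 implies a first-season placebo rate of 0.04×2/(1+0.0545) = 7.6%, above the 2% to 6% planning range. At k = 1.5 the shift is under one point of efficacy. All of that stands, and it is why this is not a major defect. It does not remove the bias. At about k = 3 the crude error passes 0.025 when the later rate is held at 4%.

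The stratified test does not deliver 0.0124 at the 0% null either: it rejects at about 0.013. That also stands, but it is small-sample behaviour shared with the crude test. Stratification removes the part that grows with k. Nor does 0.0124 apply to the secondary endpoints, which use the lower bound of a two-sided 95% interval. There the bias factor carries over, but no error rate was calculated.

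The size of the 1:1 period comes from rounded targets. Moving the placebo target by 10 gives n = 112 or 232 instead of 172. At k = 2 a true 30% would then read as 1 − 0.70×(1+56/3,048)/(1+56/1,552) = 31.2%, or 1 − 0.70×(1+116/3,028)/(1+116/1,572) = 32.3%. The conclusion is unchanged.

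Finally, the Appendix 1 wording sits in a report on the superseded design, and SAP 18.3 records a correction of its later seasons to 2:1. So the conflict is editorial, but it bears on how the stratum is defined.

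**Conclusion.** The concern holds. The plan pools two allocation periods without accounting for them, and the nominal 0.0124 level is assured only if the attack rate is the same in both. With about 3.7% of infants in the 1:1 period, the effect is small: roughly one point of efficacy at a 1.5-fold rate ratio and two points at 2-fold, near the 30% margin. A higher first-season rate favours the vaccine and a lower one works against it, and the documents do not say which applies. The figures rest on the assumed k, on the back-solved size of the 1:1 period, and on a relative risk common to both periods. This change should be made because it removes a known bias at almost no cost. It does not call the design into question.

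**What to change.** In SAP 10.3, 10.4 and 16.3, and in protocol 10.4.3:

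- Add one term, allocation period (1:1 or 2:1), to the robust-variance Poisson model for the primary and secondary efficacy endpoints, taken from the randomisation record.
- Name a period-stratified Mantel-Haenszel relative risk as the fallback if the 1:1 period has no events. That chance is about 1.4% at k = 1 and 11% at k = 0.5 (4% placebo rate, 65% efficacy). Such a stratum then contributes nothing and the estimate still exists.
- State that a common relative risk across periods is assumed, and keep the unadjusted estimate as a sensitivity analysis.
- Reconcile SAP Appendix 1, section 1.0, with SAP section 2 and protocol 3.1 on when 1:1 allocation ended.

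The cost is wording plus one variable already held, and about 0.2 points of power when the rates are equal.

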3.6 Randomization and Blinding Procedure

Maternal subject randomization will be conducted using an Interactive Web Randomization System (IWRS). The system will ensure proper distribution of maternal subjects across group assignments. Stratification will be based on study site and age (18 to < 29 years and 29 to 40 years), in order to distribute the proportion of such subjects in each age group equally across treatment groups. At maternal randomization, the infant of that mother-infant pair will also be randomized to one of three phlebotomy cohorts.

Preparation and administration of the RSV F vaccine and placebo will be performed by an unblinded vaccine administrator(s), with masking of the syringe content. Administration of the RSV F vaccine and placebo will be performed by designated site personnel.

Maternal subjects and the main study team clinical staff will remain blinded as to treatment assignment for the duration of the study unless emergency unblinding is necessary. Refer to Section 3.7 for information regarding the process for emergency unblinding. However,

assignment with regard to the infant's phlebotomy cohort will be transmitted immediately to site personnel.

All treatment assignments, vaccine and placebo storage and accountability, and/or dosing related matters, will be monitored by a designated "unblinded monitor." Any deviations will be discussed, documented and resolved by the unblinded monitor and the unblinded site personnel. The unblinded monitor will be responsible for escalating issues to the clinical project team in a blinded manner. The Clinical Supplies Manager at Novavax will be responsible for determining whether the team will be unblinded in order to adequately resolve issues. Any unblinding of the project team will be clearly documented in the Trial Master File (TMF). No reports from the unblinded monitor will be released to the TMF until database lock for the final analysis and official declaration of unblinding is given by Novavax.

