Randomization of maternal subjects will be done at the site level and will be stratified by age (i.e., 18 to < 29 years and 29 to \leq 40 years). No specific proportion in either age group will be sought, rather the intent of stratification will be to distribute the proportion of maternal subjects presenting for enrollment in each age group equally across the two treatment arms. In addition, infant subjects born to randomized maternal subjects will be prospectively and randomly assigned to one of three postpartum phlebotomy cohorts, which will differ only in the timing of blood sampling.

It is anticipated that a percentage of the randomized maternal subjects and their delivered infants may not complete the study; subjects (maternal and infant) who withdraw or are discontinued will not be replaced.

All maternal subjects will receive a single IM injection on Day 0 with the assigned test article, the RSV F vaccine or saline placebo (see [Table 1](#)). For each maternal subject, study participation will span approximately nine (9) months from the first dose, ending six (6) months post-delivery. Study follow-up for infant subjects who are consented will span approximately one (1) year post-delivery (Refer to the Appendix 1 of study protocol). The DSMB will supervise enrollment and monitor subject safety throughout the trial.

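### Randomization is stratified by site and maternal age but the efficacy models use treatment alone, so a little precision is lost, and pooling 1:1 and 2:1 allocation leaves the relative risk not strictly protected

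*SAP*

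**What the plan says.** **Randomization.** Protocol Section 3.6: "Stratification will be based on study site and age". SAP Section 2 agrees: "Randomization of maternal subjects will be done at the site level and will be stratified by age". The age strata are 18 to under 29 and 29 to 40 years.

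**Analysis.** SAP Section 10.3 estimates the RR by modified Poisson regression with a log link and robust variance: "The explanatory variables in the model will include the treatment group". Section 10.4 repeats this for the secondary endpoints. The word for the model terms might leave room for others, but Section 16.3 closes it: "No covariate adjustment will be made in the primary and secondary efficacy and immunogenicity endpoint analyses". Maternal age returns there only as a subgroup factor, beside World Bank income category. Site is named in no efficacy analysis, and no reason is given for leaving the randomization factors out.

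**Test.** "The final analysis will be carried out at one-sided Type I error rate of 0.0124". Section 16.4 sets the threshold at 30% efficacy for the US submission and 0% elsewhere.

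**Allocation.** Protocol Section 3.1: "After the first global season of enrollment, the randomization scheme will be changed to a 2:1 (active / placebo) ratio". The adaptive design report (SAP Appendix 1, Section 1.0) puts the change earlier: "During enrollment of the northern hemisphere within the first year subjects will be randomized 1:1 to vaccine or placebo and 2:1 thereafter". SAP Section 13 plans for "2,786 in the RSV F vaccine group and 1,432 in the placebo group to account for 1:1 and 2:1 randomization ratios". Neither season nor allocation period enters any planned efficacy model or listed subgroup.

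**The concern.** Randomizing within strata keeps the arms balanced on site and age, so differences in attack rate between strata largely drop out of the treatment comparison. A treatment-only model with robust variance still counts those differences as noise. The interval is then a little wider than the design earned, in a trial whose US criterion is a lower bound above 30% at one-sided 0.0124 and whose stated power at a 3% placebo rate and 65% efficacy is 76%.

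The usual reassurance is that leaving out stratification factors costs only precision, because the RR is collapsible when it is common across strata. That needs treatment to be balanced across whatever drives risk. Allocation here changed over time, so the arms hold different shares of infants from the first period. If baseline risk differed between periods, the pooled RR is itself displaced.

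**Working it through.** **Inputs.** 2,786 vaccine and 1,432 placebo infants; placebo rate 4%, RR 0.35; margin RR 0.70; one-sided 0.0124, so z = 2.2445 (SAP Sections 10.3 and 13). The documents give no site-, country- or season-specific rates for this endpoint, so the spreads below are assumptions.

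**1. Reproduce the stated power.**
- Var(log RR) = (1 − 0.014)/(2,786 × 0.014) + (1 − 0.04)/(1,432 × 0.04) = 0.02528 + 0.01676 = 0.04204; SE = 0.2050.
- Power = Φ(ln(0.70/0.35)/0.2050 − 2.2445) = 87.2%, against 87% stated. The other table cells agree to about 2 points. The plan's figure is thus an unadjusted calculation.

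**2. Gain from stratifying fully by site.** Let site rates have coefficient of variation CV, with a common RR and constant allocation. In each arm the mean of p_s(1 − p_s) is p − p²(1 + CV²), so that arm's variance term falls by CV²/n. The total reduction is CV² × (1/2,786 + 1/1,432) = CV² × 0.001057.

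| Placebo rate, efficacy | Var(log RR), treatment only | Variance ratio, CV 0.5 | Variance ratio, CV 1.0 |
|---|---|---|---|
| 4%, 65% | 0.0420 | 0.994 | 0.975 |
| 4%, 50% | 0.0343 | 0.992 | 0.969 |
| 3%, 65% | 0.0564 | 0.995 | 0.981 |

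At 4% and 65%, the SE becomes 0.2044 or 0.2024, and power 87.4% or 88.1%. If the observed efficacy were 65%, the 97.52% lower bound, 1 − 0.35 × exp(2.2445 × SE), would move from 44.5% to 44.6% or 44.9%.

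**3. Age alone.** Two equal strata whose rates differ k-fold have CV = (k − 1)/(k + 1). For k from 1.5 to 3, CV runs from 0.2 to 0.5, the SE falls by 0.05% to 0.3%, and power reaches at most 87.4%.

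**4. Effect of the allocation change.** Let n be the number of infants in the 1:1 period.
- n/2 + (4,218 − n) × 2/3 = 2,786 gives n = 156, or 78 per arm. As a cross-check, base accrual in SAP Appendix 1, Table 3 is 20 + 154 = 174 mothers in the first two hemispheric seasons; 174 × 4,218/4,600 ≈ 160.
- These infants are 78/2,786 = 2.8% of the vaccine arm and 78/1,432 = 5.4% of the placebo arm.
- With k now the ratio of first-period to later baseline risk, pooled RR / true RR = (0.028k + 0.972)/(0.0545k + 0.9455).
- The error column uses SE 0.171 (4% placebo rate, RR 0.70) and is approximate.

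| k (assumed) | Factor on RR | True efficacy of 30% reads as | One-sided error at the 30% null |
|---|---|---|---|
| 0.5 | 1.014 | 29.0% | 0.010 |
| 1 | 1.000 | 30.0% | 0.0124 |
| 2 | 0.975 | 31.8% | 0.018 |
| 3 | 0.952 | 33.3% | 0.025 |

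If 1:1 covered only the first 20 mothers, as the adaptive design report implies, then at k = 2 a true 30% reads as 30.2% and the error is about 0.013.

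**The case against.** The treatment-only analysis is explicit, pre-specified, internally consistent and in common use, and the power table rests on it. A reader might infer from the mismatch with the randomization that the primary interval is invalid or that the conclusion is at risk. The documents do not support that: at constant allocation the mismatch makes the interval slightly wide, and the lower bound in step 2 moves by less than half a point.

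A reader might also take the step 2 gains as what a workable fix would deliver. They are not. They assume a spread between sites, whereas a practical analysis must pool sites to country and cannot recover variation within a country. The number of sites and enrolment by country are not given, so the country-level gain cannot be calculated. The background on disease burden (Protocol Section 1.2) does show variation, such as 1.7 to 2.6% of US and Australian infants hospitalized in the first year against 11% of southwest Native American infants. But it mostly concerns other outcomes and age bands, and Section 1.2.4 describes its multi-country Asian estimates as fairly uniform. None of it yields a CV for this 90-day endpoint.

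These points stand and fix the size of the finding. They do not remove it: a design feature goes unused, without a reason given, and using it costs little.

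**Conclusion.** A minor, optional improvement. At a constant allocation ratio and a common RR, the treatment-only interval is valid and slightly wider than needed. Under an assumed between-site CV of 0.5 to 1.0, full site stratification would cut the variance of log RR by about 0.5% to 3% and add at most 0.2 to 0.9 points of power at the planning case. Country pooling would give less, and age alone almost nothing.

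The claim that omission leaves the RR unchanged, or always makes the interval conservative, cannot be made without a condition, because two allocation ratios are pooled. A reader might go further and infer that the RR is in fact biased or the 0.0124 level exceeded. The documents do not show this: they give no rates by period, the shift could go either way, and the 1:1 period is only about 4% of infants (156/4,218), or fewer on the adaptive design report's account.

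**What to change.** In SAP Sections 10.3, 10.4 and 16.3, before unblinding:

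- Pre-specify a single estimator: a Mantel-Haenszel RR stratified by country and maternal-age stratum (18 to under 29, 29 to 40), with allocation period (1:1 or 2:1) as a further stratum.
- Fix the country grouping in advance, without reference to outcome by arm.
- Keep the treatment-only modified Poisson model as a sensitivity analysis.
- Reconcile Protocol Section 3.1 with SAP Appendix 1, Section 1.0 on when 1:1 allocation ended, and define the period stratum from the allocation actually used.

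**Cost.** SAP wording and a modest program change. Protocol Section 10.4.3 names the Poisson model, so the departure should be recorded in SAP Section 17; Protocol Section 10.10.1 allows modifications through the SAP. The tipping-point grid in SAP Section 16.8 assigns imputed events by arm only, so it would need a rule for placing them in strata or should stay with the treatment-only model.

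**Downside.** Strata with no events, or with infants in one arm only, contribute nothing. About 96 primary events are expected at the planning case (57 placebo, 39 vaccine), of which only about four fall in the 1:1 period (78 × 0.04 + 78 × 0.014 = 4.2). Sparsity matters most for the rarer secondary endpoints and is the reason to pool sites to country.
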